The purpose of this quasi-experimental pilot study is to determine the feasibility, acceptability, and adherence to a nurse and dietitian-led web-based health education program (eCo-CHIN) to improve stress and emotional regulation in Black women with hypertension. Thirty-two women will be enrolled in 3 cohorts of 6-8.. The feedback from each cohort will be incorporated, in an iterative fashion, to improve delivery of the intervention to the following cohort.

The study aims are to:

Aim 1: Determine the feasibility, acceptability, and adherence to a synchronous web-based health education program, eCo-CHIN, to engage in Covid-19 stress management and BP self-care for Black women with hypertension.

H.1. We hypothesize that the intervention will be feasible, acceptable, and that participants will adhere to eCo-CHIN. Weekly attendance will be recorded. We will use open-ended questions after the 4-week sessions and elicit feedback from participants regarding feasibility and acceptability of eCo-CHIN. A sleep diary, self-reported physical activity, Food Frequency Questionnaire Block, and anthropometric data (weight, BMI, waist circumference) will be collected at baseline, 1 month, and 6 months.

Aim 2: Determine the initial efficacy of eCo-CHIN to reduce stress and improve emotional regulation and BP self-care (BP knowledge, resilience, mindful awareness, diet, sleep hygiene) for Black women with hypertension.

H.2. We hypothesize that there will be an improvement in perceived stress, emotional regulation, and BP self-care from baseline to post-intervention. We will collect psychosocial data using the All of Us Cope COVID-19 survey (which includes sleep, stress , and a resilience scale), Beck Anxiety and Depression measures and surveys of stress, and emotion regulation, , at baseline 1 month, and 6 months.

Aim 3: Explore the feasibility of collecting cognitive performance data (processing speed, attention, and executive function) via teleconference. The Repeatable Neuropsychiatric Battery (RBANS) will be collected at baseline and 6 months. The CAIDE will be assessed at baseline, 1 month and 6 months.

Aim 4: Explore a preliminary economic evaluation of the cost to deliver the intervention over the duration of the study. Research staff will track time and resources needed for implementing the study including personnel, training, facilities, materials, equipment, other inputs, and required client inputs monthly.

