- Cultural tailoring by use of culturally familiar terms in the educational materials, connecting mindful awareness to spirituality, and delivery of sessions in a familiar setting (home).
- The use RBANS via a web-based platform to explore the use of eCo-CHIN to enhance cognitive function (processing speed, attention, and executive function).

III. Procedures/Approach

Introduction. The theoretical framework for our intervention is adapted from the Information-Motivation-Behavioral Skills model.^{49,50} The intervention has three components that include knowledge of basic information regarding an illness/disease (hypertension), motivation through learning in a socially supportive environment (eCo-CHIN), and behavioral skills acquired to manage a chronic illness through improving self-efficacy (confidence in managing hypertension) to cope with stress and support emotional regulation. Demographic, clinical, and lifestyle factors and neurocognitive factors are proposed to influence the adoption of eCo-CHIN, stress management and emotion regulation strategies. Cognitive function is an exploratory feasibility aim to administer testing via teleconference.

A. Research Design

Quasi-experiment pre/post design to test the eCo-CHIN intervention in Black women with hypertension.

The intervention consists of four web-based weekly group sessions, lasting 90 minutes each that are delivered by a Registered Nurse (RN) and a Licensed Dietitian (LD).

B. Sample

Thirty-two Black women age 45-65 (middle-age as defined by the U.S. Census) will be enrolled in 3 cohorts (6-8 participants), with one new cohort beginning every 4-6 weeks. Inclusion criteria are English speaking, self-identification as Black/African American, diagnosis of hypertension (treated with medications and or lifestyle management), female sex, and access to a smart phone or a computer capable of connecting to the Internet (80% of Blacks have a smartphone).⁵¹ Exclusion criteria are no access to computer with internet or Smartphone or diagnosis of resistant hypertension defined as blood pressure that remains above goal despite concurrent use of three antihypertensive agents of different classes, one of which should be a diuretic/water pill.

Measurement/Instrumentation

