Table 1 displays all study measures. We have carefully chosen measures based on their appropriateness for this population, validity, reliability, and level of burden. The study team has experience with all measures. Instruments either have been used by the study team in prior work or have been pilot tested for the purpose of the proposed application. Most of the questionnaires use Likert-type scales and consist of 1-30 items averaging 10 items or less. Burden of the study procedures on participants was a major consideration in the selection of the study measures and thus, we chose measures that are short and easy to administer. Study staff will offer breaks to participants to use facilities as needed. In our previous experiences, it takes no longer than 90 minutes to complete the visit. To minimize the risk of Covid-19 transmission, all data will be

IRB Protocol Number: 2020B0182
 IRB Approval date: 06-28-2020
 Version: 11-13-2020
 2-23-2024
 5-26-2024
 10-01-2021

collected remotely and will not require in-person contact. Participants will be provided with instructions and phone support to self-collect blood pressure and anthropometric data (weight and waist circumference).

Participants will receive the links to YouTube Videos- How to take their own BP and waist measurements via email. The Weight/Waist/BP Measurement document in REDCap will be used by the research staff to record information.

Enrollment	MEASUREMENT	DATA COLLECTION			RELIABILITY/VALIDITY
		Base	1-month	6 months	
All of Us Covid Cope	Demographics, exposure, and preventative practices Demographics will not be repeated at 1 month and 6 months	X			
Education and age	Years	X			
Income	All of Us Covid Cope	X			
Alcohol use	All of Us Covid Cope	X			
Smoking	All of Us Covid Cope	X			
Comorbidities	Self-report list of chronic conditions	X			
Anthropometric measures	Waist and weight	X	X	X	
Risk factor for dementia	CAIDE	X	X	X	Sensitivity = .77, specificity= .63 and negative predictive value= .98.
Co-CHIN (4 weekly sessions)					
Information, Motivation and Behavioral Skills	Attendance and weekly check-in for adherence to eCo-CHIN homework, sleep diary, and physical activity and blood pressure logs.		X		
Outcomes					
Feasibility	Investigator generated open-ended questions		X		
Stress	All of Us Covid Cope Which contains the perceived stress scale Daily Inventory of Stressful Events	X	X	X	Cronbach α = 0.83 Cronbach α .71

IRB Protocol Number: 2020B0182
 IRB Approval date: 06-28-2020

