After completion of the 1-month data collection, participants will receive items donated by the Alcohol Drug and Mental Health (ADAMH) of Franklin County system that includes a resource directory, grocery bag that includes an ink pen, stress ball, bag clip, and hand sanitizer. Additionally, The Ohio State University James Cancer Center has donated a scarf, insulated cup, and lip gloss.

After completion of the study, at 6 months, the participant will have the option of either receiving a \$75.00 Amazon gift card or retain their self-care monitoring equipment (Home BP monitor and weight scale). If the participant selects the Amazon card, then we will provide them with a postage paid package to return the self-care equipment.

IRB Protocol Number: 2020B0182
IRB Approval date: 06-28-2020
Version: 11-13-2020
2-23-2024
5-26-2024
10-01-2021

After completion of the COVID ALL OF US COPE survey at 6 months, you will receive a \$10.00 Amazon gift card.

Participants will also waist tape measurer, pill box, and kick stand for their smartphone.

The reason for any participant's discontinuation and the date of withdrawal will be recorded in the participant's case file. The participant's case file, which will be completed up to the point of withdrawal, will be retained for five years. The study report will include reasons for participants' withdrawals as well as details relevant to the withdrawal. Each participant will be encouraged to complete the full course of the intervention assignment and study assessments. However, it is made clear to participants that they may discontinue study participation at any time for any reason. The reason for early withdrawal must be documented in the participant's case file and in the participant tracking document.

Handling of withdrawal. If a participant is withdrawn from participation in the study at any time at his or her request, or at the IRB or Principal Investigator's discretion, the reason(s) for discontinuation shall be documented thoroughly in the source documents and participant's case file. All participants who are withdrawn prematurely will undergo the procedures outlined in the discharge visit.

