The quasi-experimental design is a limitation but it is an acceptable design for a feasibility study. We will repeat measures of stress and emotion regulation over three time points (baseline, 1 month, 6 months) to reduce regression to the mean as an internal validity threat.

E. Data Analysis

IRB Protocol Number: 2020B0182
 IRB Approval date: 06-28-2020
 Version: 11-13-2020
 2-23-2024
 5-26-2024
 10-01-2021

We will use descriptive statistics to examine variable distribution, check for outliers and summarize sample characteristics and outcome measures at each time point. For Aim 1, we will use descriptive statistics to quantify the rates of recruitment, attendance, and attrition for feasibility. Using a semi-structured list of open-ended questions, we will elicit participant feedback regarding the acceptability of the intervention. The Consensual Qualitative Research Method (CQR) ⁶⁹ will be used to analyze qualitative data. The responses to open-ended questions will be transcribed. The transcripts will be reviewed by three members of the research team to determine core domains (themes).

“The preliminary lists will be presented to one another, providing examples from the transcripts. After deliberation, a list of the domains will be agreed upon. Each team member will then review the data and verify the quality of the consensually chosen domains, and subsequently meet again to discuss and arrive at a consensus on a final list of domains. Categories will be labeled based on the frequency of occurrence of themes in the data (Nguyen et al., 2013, pp. 3-5)”

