For Aim 2, we will first use descriptive statistics and trend plots to examine the outcomes (stress and emotional regulation) over time (baseline, 1-month, and 6-months). Next, Paired T-tests will be performed to examine the change of each outcome at 1-month (vs. baseline) and at 6-months (vs. baseline). Sample size from this pilot study will not have sufficient power to detect small-to-medium effect sizes for within-group difference (e.g., 54% power to detect a Cohen’s d of 0.5 with a two-sided significance level of 0.05). Therefore, we will not rely on statistical significance. Instead, we will estimate point estimates, 95% confidence intervals and effect sizes. These estimates along with clinical significance will guide our results interpretation and inform the sample size determination for a future NIH funding mechanism. For Aim 3, changes in RBANDS measure will be analyzed using the same approach for Aim 2 (baseline and 6 months). For Aim 4, Co-I [name], Health Economist, will use descriptive statistics, trends, and plots to evaluate allocations of resources and estimate costs of the intervention at various stages.

F. Project Timeline

The development of this group-delivered intervention will be an iterative process, and we will use this pilot data to submit an external grant for a 12-week intervention through the National Institutes on Aging in 12-18 months.

Table 2. Project timeline.

Activity	1-2 months	3-4 months		5-6 months	7-8 months	9-10 months	11-12 months
IRB application	X						
Recruitment		X		X			
Data collection (baseline, 1-month, 6-months)		X		X	X	X	
Delivery of Intervention		X		X	X		
Preliminary data analysis of baseline data for an NIH grant in February 2022				X	X	X	X
Final data analysis						X	X
Dissemination							X

IRB Protocol Number: 2020B0182
IRB Approval date: 06-28-2020
Version: 11-13-2020
2-23-2024
5-26-2024
10-01-2021

References

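### Aim 3 asks whether cognitive testing by teleconference is feasible, but the only analysis assigned to it is RBANS change, which does not estimate feasibility

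*Combined protocol and SAP*

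**What the plan says.** The Objectives state: "Aim 3: Explore the feasibility of collecting cognitive performance data (processing speed, attention, and executive function) via teleconference". The Introduction to Procedures/Approach repeats it: "Cognitive function is an exploratory feasibility aim to administer testing via teleconference". On timing, the Objectives say: "The Repeatable Neuropsychiatric Battery (RBANS) will be collected at baseline and 6 months". Table 1 likewise marks cognitive function at baseline and 6 months.

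The one sentence on Aim 3 in Data Analysis (III.E) is: "For Aim 3, changes in RBANDS measure will be analyzed using the same approach for Aim 2 (baseline and 6 months". The Aim 2 approach starts with descriptive statistics and trend plots, then uses paired t-tests. Interpretation rests on point estimates, 95% confidence intervals and effect sizes rather than on significance.

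Feasibility is handled elsewhere. Data Analysis assigns the rates of recruitment, attendance and attrition to Aim 1. The participant questions also sit under Aim 1: "We will use open-ended questions after the 4-week sessions and elicit feedback from participants regarding feasibility and acceptability of eCo-CHIN". The Feasibility row of Table 1 lists "Investigator generated open-ended questions", marked at 1 month only.

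**The concern.** The aim and its analysis address different quantities. Feasibility asks how many of the enrolled women could be tested remotely, on which occasion, with which test, and what stopped the others. A score change asks whether performance moved among women who have scores.

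The question has substance here because the battery was altered for remote use. The Exploratory outcome text removes the figure drawing and coding tasks and brings in SAGE and the oral trail making test. The pilot is also meant to support a grant application for a longer intervention. If the plan is followed as written, the result reported under Aim 3 would be a change in RBANS. The reader planning the next study would have to piece completion together from sources not set up for that purpose, and a reason not noted at the time of testing may not be recoverable.

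**Working it through.** **Plan's own figure.** The plan states no expected completion rate or other figure for Aim 3 feasibility, so there is none to reproduce. The 54% power in Data Analysis belongs to the Aim 2 comparison, and nothing here rests on it.

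**Step 1. Does RBANS change determine completion?** Take a standardized mean change of 0.5 (an illustration) among n women with both scores. Its 95% CI is 0.5 ± t(0.975, n−1)/√n. Set this beside the exact (Clopper-Pearson) 95% CI for n out of 32 enrolled:

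- n = 32: 0.5 ± 2.040/5.657 = 0.139 to 0.861. Completion is 100%, CI 89.1% to 100%.
- n = 16: 0.5 ± 2.131/4 = −0.033 to 1.033. Completion is 50%, CI 31.9% to 68.1%.
- n = 10: 0.5 ± 2.262/3.162 = −0.215 to 1.215. Completion is 31%, CI 16.1% to 50.0%.

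The same estimated change fits completion anywhere from 31% to 100%. A paired n printed beside the estimate would count women with both scores. It would not separate a failed baseline test, a withdrawal and a failed 6-month test, and it would cover RBANS only.

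**Step 2. Does another part of the plan supply the feasibility result?**

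- *Opening of Data Analysis:* descriptive statistics will "summarize sample characteristics and outcome measures at each time point". Cognitive function is listed among the outcomes in Table 1, so an n at baseline and 6 months would ordinarily appear. No denominator and no definition of a complete test is given.
- *Recruitment tracking (under Data Validity/Integrity):* the team will count how many women complete the first assessments, and will log whether and when data collection was done at each time point. Neither is stated to be by test. The Procedures overview lets surveys and cognitive testing fall on different days, so such an entry need not identify the cognitive test.
- *SAGE portal:* scores are stored by participant ID, so SAGE completion can be derived. This does not cover the other tests.
- *Aim 1 attrition and withdrawal records:* under Retention Plans, the reason for a participant's "discontinuation and the date of withdrawal will be recorded". This covers women who leave, not those who stay but do not complete a test.
- *Participant questions:* asked once, at 1 month. They may follow baseline testing but cannot cover testing at 6 months. The remote procedures listed under Primary outcome are smartphone use and self-collected weight, blood pressure and waist, not cognitive testing.
- *Field Notes:* staff may comment on an encounter, and a thematic analysis is planned. The notes are optional.

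No item is both test-specific and assigned to Aim 3. No section states that the device used, or the reason a test was not completed, is recorded systematically.

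**Step 3. Precision of the missing summary.** The documents give 32 women, but also 3 cohorts of 6-8, which is 3 × 6 = 18 to 3 × 8 = 24. If all n complete, the exact lower 95% limit is 0.025^(1/n):

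- n = 32: 0.025^(1/32) = 0.891
- n = 24: 0.025^(1/24) = 0.858
- n = 18: 0.025^(1/18) = 0.815

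At lower completion the interval is wider: 24 of 32 gives 56.6% to 88.5%. These counts illustrate precision; they are not predictions.

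**The case against.** The best case for the plan is that the information is largely there and only the label is missing. Baseline cognitive testing belongs to the initial visit, and the plan undertakes to count women who complete the first assessments. Summaries at each time point would show how many have cognitive data. SAGE completion can be read from the portal, and field notes may capture difficulties. The change analysis also has a purpose: the Innovation list proposes using RBANS to explore whether the programme enhances cognitive function. The aim is exploratory, and no primary conclusion depends on it.

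Most of this stands, and it limits the point. What it does not supply is a result, by test and with a denominator, that is assigned to Aim 3, or a systematic record of why tests fail.

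Three stronger readings are tempting and are not supported:

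- A reader might infer that the plan would yield no count of women tested and no recorded reason. The tracking, the general summaries, the portal and the field notes say otherwise, especially at baseline. The gap is in assignment and system.
- A reader might infer that the RBANS change analysis should be dropped. It serves the stated innovation and can stay.
- A reader might infer that the two loan iPads cap testing at 2/8 = 25% to 2/6 = 33% of a cohort, because a smartphone is enough to enrol while SAGE is taken on a touch screen tablet or computer. No section says a cohort is tested at the same time, and no number of women without a suitable device is given. The constraint would in any case concern SAGE, not RBANS.

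**Conclusion.** The mismatch holds. Aim 3 is worded twice as a feasibility question, and the only analysis assigned to it does not estimate feasibility. It should be corrected because the correction is cheap and makes a stated aim answerable. The consequence is limited to that exploratory aim.

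The conclusion rests on the documents as they stand. The REDCap forms and the open-ended question list are not reproduced there, so device or reason fields may exist without being described. The precision figures assume full completion, or the stated illustrative counts, because no expected rate is given.

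**What to change.** 1. Reconcile the battery first. The Exploratory outcome text names RBANS, Trail Making A and B, COWAT, Stroop, SAGE and oral trail making; Table 1 names RBANS, Oral Trail Making and SAGE. Because two tasks are removed for remote use, state which remaining parts make up the RBANS.
2. Define *complete* and *scorable* for each test before analysis.
3. Make the main Aim 3 summary the proportion of all enrolled women with a complete, scorable remote assessment at baseline and at 6 months, by test and overall, with an exact 95% CI. Use the number actually enrolled as the denominator.
4. Record the device used and the reason for any non-completion in REDCap at the time of testing.
5. Keep the RBANS change estimates with 95% CIs as secondary and descriptive.

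The cost is SAP wording, one or two tables and a few REDCap fields. No new visit is needed, and SAGE completion can already be taken from the portal.

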We established a BUSINESS ASSOCIATE AGREEMENT with BrainTest, INC SEZC to obtain access to the Self-Administered Gerocognitive Screen online. Participants shall only be able to access their BrainTest on submission of a unique Identification number to be created by OSU (the "ID"). BrainTest shall not accept any personally identifiable information from any of the Participants. BrainTest will provide the following:

1. BrainTest shall provide OSU with a unique internet URL where only the Participants shall have access to take the BrainTests from OSU's or the Participants' own touch screen tablets or touch screen computers.
2. BrainTest shall develop a web based portal for the recording of all Participants BrainTests scores (the "Portal"). The Portal shall be password protected and shall be for the sole use of OSU. OSU shall be able to download all data in the Portal in .xls format, at any time prior to the termination of this Agreement.
3. BrainTest shall use its Core Scoring Lab to score all the BrainTests submitted by the Participants. All the scoring of the Participants' BrainTests shall be completed within 48 hours of the BrainTests being submitted by the Participants. All Participants' scores shall be uploaded to the Portal by BrainTest using each Participants' ID as the identifier.

Advisory Board

We will rely on the Advisory Board to assist us with accessing the community by making introductions of study staff to key community leaders and members and identifying community assets (e.g., resources, organizations) to support the project. The Advisory Board will have a role in tailoring of the intervention and recommendations to promote sustainability of the project, dissemination, and problem-solving with the research team. The Community Advisory Board will meet monthly via Zoom, more if needed. We will work closely with the Community Advisory Board to ensure that our de-identified summary of findings are fair and accurate and provide input on how best to disseminate the results back to the community. The Study PI is in charge of the meetings and no participant information will not be shared with the Advisory Board.

IRB Protocol Number: 2020B0182
IRB Approval date: 06-28-2020
Version: 11-13-2020
2-23-2024
5-26-2024
10-01-2021

Detailed study procedures

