- If the person says no, then they will be thanked for their time.
4. If the person checks yes, another box would open to request their contact information (phone, email, mailing address) and query as to whether or not they want documentation linking them to the research.
 5. We will contact the participant to confirm eligibility for the study, answer any questions they may have about the consent form, verify verbal consent (logged in REDCap), and schedule the first study visit. We will mail a copy of the consent form to the participant for their records.

Baseline survey data will be collected as listed in Table 1. Data will be collected using a private room via phone or Zoom secure video conference. The participant can enter by invitation only. If the participant does not have access to a touch screen tablet or computer, they may be able to borrow one of our two iPads from the College of Nursing. This would be mailed to the participant with return postage paid.

1. Meetings will require a password by default. These passwords will be embedded in the meeting URL (link) by default.
2. Annotations will not be available to participants by default.
3. The ability to join a meeting before the host or alternate host joins will be disabled by default.
4. Participants will not be able to change their names by default.
5. The questions to surveys will be read to the participant and answers recorded on survey forms and entered into REDCap under the participant's study ID number. Response cards will be given to participants to follow along with the interviewer.

In the future, we may have similar research studies. The consent form will also include the opportunity for participants to partner with us for potential future studies that are related to hypertension and health in Black and African Americans. The scope of the request for the participant's contact information will be access to the following by the study team/PI:

The contact information will not be provided to other investigators for similar research projects without further informed consent (e.g., recruitment registry).

- a. First and last name.
- b. Address
- c. Phone number (cell/home)

IRB Protocol Number: 2020B0182
IRB Approval date: 06-28-2020
Version: 11-13-2020
2-23-2024
5-26-2024
10-01-2021

d. Email

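### The Aim 3 change in RBANS score from baseline to 6 months is true change plus any practice gain, and nothing in the plan separates the two

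*Combined protocol and SAP*

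**What the plan says.** **Design.** Section III.A describes a "Quasi-experiment pre/post design to test the eCo-CHIN intervention in Black women with hypertension". There is no comparison group.

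**Schedule.** Section I (Aim 3) and Table 1 place the RBANS at baseline and 6 months only.

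**Analysis.** Section III.E: "For Aim 3, changes in RBANDS measure will be analyzed using the same approach for Aim 2 (baseline and 6 months". For Aim 2 the same section says: "Paired T-tests will be performed to examine the change of each outcome at 1-month (vs. baseline) and at 6-months (vs. baseline". It then sets significance aside in favour of point estimates, 95% CIs and effect sizes. Together with clinical significance, these are to guide interpretation and help size a future study. That sentence is written under Aim 2 and reaches Aim 3 through the same-approach wording.

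**Purpose.** Section I and the introduction to Section III present cognition as an exploration of whether testing by teleconference is feasible. The Innovation list in Section II goes further: "The use RBANS via a web-based platform to explore the use of eCo-CHIN to enhance cognitive function".

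**Safeguards.** Section III.D accepts the quasi-experimental design as a limitation. It offers repeated measurement against regression to the mean, for stress and emotion regulation only. Practice, alternate versions and practice-adjusted analysis appear nowhere. The word Repeatable in the test's name is not a stated plan to change versions.

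**Devices.** Eligibility (Section III.B) asks for "access to a smart phone or a computer capable of connecting to the Internet". The online SAGE is taken on the university's or participants' "own touch screen tablets or touch screen computers". A woman without a touch screen is told that "they may be able to borrow one of our two iPads". No rule asks for the same device at both tests or for a record of which was used.

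**The concern.** Someone who takes a cognitive battery a second time knows the tasks and may remember items, so her score can rise with no change in cognition. A control group would show that rise and allow it to be subtracted. Here there is none, so the mean paired change absorbs it in full.

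Two uses of the estimate are exposed. A positive change could be read as support for the Innovation statement on enhancing cognition. An effect size inflated by practice, if carried into the sample size of a later study, would make that study too small.

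**Working it through.** **1. What the estimate contains.** In a single group, mean change = true change + practice gain + sampling error. With zero true change, its expected value is the practice gain.

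**2. The plan's own figure.** Section III.E gives one number for this analysis: 54% power at d = 0.5, two-sided 0.05. An exact paired t-test (noncentral t, df = n − 1, noncentrality d√n) gives 78.2% at n = 32 and 54.1% at n = 19. So 54% does not follow from 32 women. That mismatch is a separate matter, and this point does not depend on it. It is the only reason n = 19 appears below; the documents never state 19.

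**3. Inputs for the illustration.**
- n = 32 (Section III.B).
- r = .70 (Table 1, cognitive function row). The table labels it as either test-retest or inter-rater and ties it to no interval. Using it as the baseline-to-6-month correlation is an assumption.
- Practice gain g = 0.1 to 0.4 baseline SD. The documents give no value; the range is assumed.
- Equal SDs at the two tests (assumed).

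**4. Precision.**
- SD of change = √(2 × (1 − 0.70)) = √0.60 = 0.775 SD.
- Standard error = 0.775 / √32 = 0.137 SD.
- 95% CI half-width = 2.04 × 0.137 = 0.279 SD.

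An observed gain above about 0.28 SD therefore gives a CI that excludes zero.

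**5. Effect of practice with no true change.** The standardised shift is g / 0.775 and the noncentrality is that shift times √n. For g = 0.3 and n = 32: 0.3 / 0.775 = 0.387, and 0.387 × 5.657 = 2.19. The probability that the whole CI lies above zero is:

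| Assumed practice gain (SD) | n = 32 | n = 19 |
|---|---|---|
| 0.1 | 10.5% | 7.7% |
| 0.2 | 29.3% | 18.6% |
| 0.3 | 56.5% | 35.9% |
| 0.4 | 80.8% | 56.8% |

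With no practice gain the figure is 2.5% in this direction.

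**6. Sensitivity to the correlation.** For a 0.3 SD gain at n = 32, the probability is 37.6% at r = .5, 56.5% at r = .7 and 73.9% at r = .8.

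**The case against.** **It is an exploratory feasibility aim.** Section I states hypotheses for Aims 1 and 2 and none for Aim 3, and the test battery is headed as an exploratory outcome. This stands and lowers the weight of the point. It does not remove it, because Section III.E goes beyond completion of testing and estimates change in scores.

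**Significance will not be relied on.** True, and a CI that excludes zero is a significance criterion in another form, so the table above only shows scale. The bias in the point estimate and effect size remains whatever criterion is used.

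**Exposure is already limited.** Cognition is not tested at 1 month, while stress, emotion and diet are measured three times. Two sittings six months apart do limit practice. The plan does not give that as the reason, and a second sitting is still a repeat.

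**The grant may not use the change score.** Table 2 ties the February 2022 application to baseline data, which contain no change score. That weakens the risk for that application. Section III.E still speaks of using the estimates to size future work.

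**Devices.** A reader might infer that switching screens between visits also inflates the apparent benefit. The documents do not support this. The touch-screen requirement belongs to SAGE, for which no change analysis is stated, and the sentence on Aim 3 analysis covers the RBANS only. No passage says that a woman would switch device, and a switch could move scores either way.

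**Conclusion.** The point holds at modest weight. As planned, the RBANS change cannot distinguish practice from true change, and the plan does not say so. That conclusion follows from the design and needs no numerical assumption.

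The size does need assumptions. With n = 32, a 6-month correlation of .70 and a practice gain between 0.1 and 0.4 SD, a CI wholly above zero would arise in 10% to 81% of trials with no true effect. The width of that range shows how little the documents fix. It should not be quoted as this trial's false-positive rate.

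A reader might also infer that practice pushes towards a hypothesised result. Section III.E and the aims do not support that wording, since Aim 3 has no hypothesis. The expectation of better cognition comes from the Purpose text and the Innovation list. For SAGE, an uncontrolled device is a source of added error if change is ever reported, not a bias towards benefit.

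**What to change.** 1. **Exploratory outcome paragraph (Section III.C).** For each cognitive test that has an alternate version, give a different version at 6 months and balance the starting version across women. The documents name no such test, so the team must confirm which qualify, including for the shortened remote battery. This reduces memory for items but not familiarity with the task, so practice is reduced and not removed.
2. **Section III.E, Aim 3.** State that cognitive change will be reported as change including practice, will not be attributed to eCo-CHIN, and will not be used unadjusted to size a future study.
3. **Innovation list (Section II).** Reword the RBANS item to match the feasibility aim.
4. **Secondary, SAGE only.** If SAGE change is to be reported, record the device and use the same one at both tests, booking a loan iPad for both dates where one is needed.

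**Cost.** Items 2 and 3 are wording changes and prevent most of the harm. Item 1 needs scheduling and adds a little noise from differences between versions; balancing the starting version removes these from the mean change. For example, if two versions differed by an assumed 0.1 SD, the variance of change would rise from 0.60 to 0.60 + 0.1² = 0.61, and its SD from 0.775 to 0.781. Item 4 is one data field and some booking. No control arm or extra visit is needed.
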